8.3.2.1.1. Part A

BP and PR will be taken before blood collection for laboratory tests and consist of a single measurement of PR and 3 BP measurements (3 consecutive BP readings will be recorded at intervals of at least 2 minutes apart) on Day 1 pre-dose. A single BP measurement will be taken at all other visits. If systolic BP is \geq 140 or 150 mm Hg (based on age) or diastolic \geq 90 mm Hg, the BP should be repeated 2 more times and the average of the 3 BP readings will be recorded on the CRF.

8.3.2.1.2. Part B

BP and PR will be taken before collection for laboratory tests and consist of a single BP and PR measurement.

8.3.2.2. Respiratory Rate

8.3.2.2.1. Part A

RR will be measured after approximately 5 minutes of rest in a semi-recumbent or seated position by observing and counting the respirations of the participant for 30 seconds and multiplying by 2. When BP is to be taken at the same time, respiration measurement will be done during the 5 minutes of rest and before BP measurement.

8.3.2.2.2. Part B

RR measurements will be assessed in a semi-recumbent or seated position after approximately 5 minutes of rest. RR findings collected during the study will be collected on the CRF for Part B.

8.3.2.3. Oxygen Saturation: Part B-Participants with PAH

Oxygen saturation will be collected at times specified in the SoA by pulse oximetry and findings collected during the study will be collected on the CRF.

8.3.2.4. Temperature: Part A Only

Temperature will be measured by an oral, tympanic, forehead or temporal artery method, provided the same method is used consistently throughout the study. No eating or drinking is allowed for 15 minutes prior to the measurement. Smoking is not allowed for 2 hours prior to the measurement.

8.3.3. Electrocardiograms

Standard 12-lead ECGs will be collected at times specified in the SoA section of this protocol using an ECG system that automatically calculates the HR and measures PR, QT, QTcF, and QRS intervals. All scheduled ECGs should be performed after the participant has rested quietly for at least 5 minutes in a supine position.

For single ECGs: To ensure safety of the participants, a qualified individual at the investigator site will make comparisons to baseline measurements. Additional ECG monitoring will occur if a) a post-dose QTcF interval is increased by ≥ 60 ms from the baseline and is >450 ms; or b) an absolute QT value is ≥ 500 ms for any scheduled ECG. If either of these conditions occurs, then 2 additional ECGs will be collected approximately 2 to 4 minutes apart to confirm the original measurement. If the QTcF values from these repeated ECGs remain above the threshold value, then a single ECG must be repeated at least hourly until QTc values from 2 successive ECGs fall below the threshold value that triggered the repeat measurement.

For triplicate ECGs: To ensure safety of the participants, a qualified individual at the investigator site will make comparisons to baseline measurements. Additional ECG monitoring will occur if a) the mean value from the triplicate measurements for any post-dose QTcF interval is increased by ≥ 60 ms from the baseline **and** is ≥ 450 ms; or b) an absolute QT value is ≥ 500 ms for any scheduled ECG. If either of these conditions occurs, then a single ECG measurement must be repeated at least hourly until QTcF values from 2 successive ECGs fall below the threshold value that triggered the repeat measurement.

If a) a post-dose QTcF interval remains ≥ 60 ms from the baseline and is >450 ms; or b) an absolute QTcF value is ≥ 500 ms for any scheduled ECG for greater than 4 hours (or sooner, at the discretion of the investigator); or c) QTcF values get progressively longer, the participant should undergo continuous ECG monitoring. A cardiologist should be consulted if QTcF values do not return to less than the criteria listed above after 8 hours of monitoring (or sooner, at the discretion of the investigator).

In some cases, it may be appropriate to repeat abnormal ECGs to rule out improper lead placement as contributing to the ECG abnormality. It is important that leads be placed in the same positions each time in order to achieve precise ECG recordings. If a machine-read QTc value is prolonged, as defined above, repeat measurements may not be necessary if a qualified medical provider's interpretation determines that the QTcF values are in the acceptable range.

ECG values of potential clinical concern are listed in Appendix 8.

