- 17. Systolic BP < 90 mmHg during Screening or at baseline.
- 18. ECG with QTcF >490 msec during Screening or Randomization.
- 19. Any of the following clinical chemistry values during Screening:
 - ALT or AST > $3 \times$ ULN (> 5 ULN if solely due to right heart failure) or total bilirubin $\ge 2 \times$ ULN (For Gilbert's syndrome, direct bilirubin >ULN [or $\ge 2 \times$ ULN if solely due to right heart failure] is exclusionary).

- eGFR < 30 mL/min/1.73 m2 within 30 days prior to randomization or required renal replacement therapy within 90 days of randomization.
- 20. Hematologic abnormalities defined as:
 - Platelets \leq 50,000/mm³

Other Exclusion Criteria:

- 21. A positive urine drug test. A single repeat for positive drug screen may be allowed. A positive test for cannabinoid-based compounds (eg, THC, CBD, etc) will not be considered exclusionary.
- 22. Participants with a diagnosis of COPD or other clinically significant lung disease.
- 23. Investigator site staff directly involved in the conduct of the study and their family members, site staff otherwise supervised by the investigator, and sponsor and sponsor delegate employees directly involved in the conduct of the study and their family members.

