7.1.3. ECG Changes

A participant who meets either bulleted criterion based on the average of triplicate ECG readings will be withdrawn from the study intervention.

- QTcF >500 ms.
- Change from baseline QTcF >60 ms and QTcF >450 ms.

If a clinically significant finding is identified (including, but not limited to, changes from baseline in QTcF after enrollment), the investigator or qualified designee will determine if the participant can continue in the study and if any change in participant management is needed. This review of the ECG printed at the time of collection must be documented. Any new clinically relevant finding should be reported as an AE.

PFIZER CONFIDENTIAL CT02-GSOP Clinical Protocol Template Phase 1 2 3 4 (14 April 2023) Page 92

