8.3.3.2. Part B

Single ECGs will be collected as per SoA. A triplicate ECG will be collected on Day 1. ECGs should be performed prior to 6MWT.

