9.3.5.1. Electrocardiogram Analyses

Changes from baseline for the ECG parameters HR, QTcF, PR interval, and QRS interval will be summarized by treatment and time. The frequency of uncorrected QT values above 500 ms will be tabulated.

The number (%) of participants with maximum postdose QTcF values and maximum increases from baseline in the following categories will be tabulated by treatment:

Safety QTcF Assessment

Degree of Prolongation	Mild (ms)	Moderate (ms)	Severe (ms)
Absolute value	>450-480	>480-500	>500
Increase from baseline		30-60	>60

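### The absolute limb of the repeat-ECG trigger is set on uncorrected QT, while withdrawal and continuous monitoring use QTcF, so in some Part B participants a single QTcF above 500 ms mandates no confirmatory tracings

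*Protocol*

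**What the plan says.** Protocol section 8.3.3 has one trigger paragraph for single ECGs and one for triplicates. Each has two limbs. Limb (a) is a QTcF rise of at least 60 ms together with a QTcF threshold of 450 ms. Limb (b), in both paragraphs, is that "an absolute QT value is ≥ 500 ms for any scheduled ECG". For single ECGs, meeting either limb requires two more tracings 2 to 4 minutes apart.

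What follows the trigger is stated in corrected QT:

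- Single-ECG repeats (8.3.3): "If the QTcF values from these repeated ECGs remain above the threshold value", hourly ECGs follow.
- Triplicate paragraph (8.3.3): hourly ECGs continue "until QTcF values from 2 successive ECGs fall below the threshold value that triggered the repeat measurement".
- Continuous monitoring (8.3.3): the absolute criterion is that "an absolute QTcF value is ≥ 500 ms for any scheduled ECG for greater than 4 hours".
- Withdrawal (7.1.3): "A participant who meets either bulleted criterion based on the average of triplicate ECG readings will be withdrawn from the study intervention". The absolute criterion there is QTcF above 500 ms.

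Two Part B features matter. Section 8.3.3.2 says "Single ECGs will be collected as per SoA. A triplicate ECG will be collected on Day 1". Section 5.4 excludes only an "ECG with QTcF >490 msec during Screening or Randomization", so a baseline QTcF up to 490 ms is eligible.

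**The concern.** The trigger and the actions that depend on it are measured on different scales. Above 60 bpm QTcF is larger than QT, so a tracing can exceed 500 ms on the scale used for withdrawal while staying below 500 ms on the scale used for limb (b). Limb (a) covers that tracing only if the rise from baseline is at least 60 ms. A participant who enters with a long QTcF can cross 500 ms on a smaller rise.

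In Part B every scheduled ECG after Day 1 is a single tracing, and the two extra tracings of 8.3.3 are the only mandated way to get from one tracing to the three on which 7.1.3 judges withdrawal. If neither limb fires, a reading above the withdrawal value does not by rule lead to that judgement. The participants affected are those with the longest baseline QTcF.

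Section 8.3.3 is also inconsistent within itself. A repeat prompted by limb (b) is judged by comparing QTcF with the threshold that prompted it, but that threshold is a QT.

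**Working it through.** **Inputs.** Limb (a): QTcF rise of at least 60 ms and QTcF above 450 ms (8.3.3). Limb (b): QT of at least 500 ms (8.3.3). Withdrawal: QTcF above 500 ms on a triplicate average (7.1.3). Largest eligible Part B baseline: QTcF 490 ms (5.4). The protocol names Fridericia's correction, QTcF = QT / (60/HR)^(1/3), so QT = QTcF × (60/HR)^(1/3). It gives no heart-rate distribution, so the rates below are assumed and shown as a range.

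**Step 1: when limb (a) is silent above 500 ms.** The rise must be under 60 ms with QTcF above 500 ms, so baseline must be above 500 − 60 = 440 ms.

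**Step 2: when limb (b) is silent.** QT is below 500 ms when HR exceeds 60 × (QTcF/500)^3:

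| QTcF (ms) | HR above which QT < 500 ms (bpm) |
|---|---|
| 510 | 63.7 |
| 520 | 67.5 |
| 530 | 71.5 |
| 540 | 75.6 |
| 550 | 79.9 |

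Equivalently, limb (b) first fires at QTcF = 500 × (HR/60)^(1/3): 470.5 ms at 50 bpm, 500 at 60, 513.5 at 65, 526.4 at 70, 538.6 at 75 and 550.3 at 80.

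**Step 3: how far past 500 ms the first mandatory repeat comes.** The trigger is met at the lower of baseline + 60 and the limb (b) value, so the excess is max(0, min(baseline + 60, 500 × (HR/60)^(1/3)) − 500), in ms:

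| Baseline QTcF (ms) | 60 bpm | 65 bpm | 70 bpm | 75 bpm | 80 bpm |
|---|---|---|---|---|---|
| 440 or less | 0 | 0 | 0 | 0 | 0 |
| 450 | 0 | 10 | 10 | 10 | 10 |
| 460 | 0 | 13.5 | 20 | 20 | 20 |
| 470 | 0 | 13.5 | 26.4 | 30 | 30 |
| 480 | 0 | 13.5 | 26.4 | 38.6 | 40 |
| 490 | 0 | 13.5 | 26.4 | 38.6 | 50 |

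Fifty ms is the maximum, because limb (a) fires at 490 + 60 = 550 ms at the latest.

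**Step 4: one case in full.** Baseline 460 ms, post-dose single tracing QTcF 510 ms at 80 bpm. The rise is 510 − 460 = 50 ms, under 60, so limb (a) is silent. QT = 510 × (60/80)^(1/3) = 463 ms, under 500, so limb (b) is silent. The tracing is above the 500 ms used for withdrawal and no repeat is required.

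**Step 5: below 60 bpm.** The mismatch reverses. At 50 bpm a QT of 500 ms is a QTcF of about 471 ms, so repeats begin at a QTcF already below 500 ms.

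**Step 6: after the fix.** With limb (b) at QTcF of at least 500 ms, the excess in Step 3 is zero for every baseline and heart rate.

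**The case against.** The strongest reply is that this is a drafting slip with little practical reach.

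- **The rules are not expressly linked.** Section 7.1.3 does not say its triplicate must come from the 8.3.3 repeats, and a single tracing of 510 ms does not itself meet 7.1.3. That is right as far as it goes. However, after Day 1 nothing else in Part B mandates three tracings.
- **A site would probably repeat anyway.** Section 8.3.3 later speaks of a prolonged machine-read QTc as though the trigger had been defined in QTc. Section 7.1.3 requires documented review of each ECG. Appendix 8 lists QTcF above 500 ms as a possible SAE and recommends such findings as alerts. These make it unlikely that the value goes unnoticed, but none of them requires the two tracings. The 8.3.3 remark about machine-read values only allows repeats to be waived.
- **The reach is small.** This stands. Long baseline, QTcF above 500 ms, a rise under 60 ms and a sufficient heart rate must coincide, among about 36 participants of whom half receive active drug. While dosing continues (last dose Week 20), the scheduled post-dose ECGs are Day 8 and Week 12. How many participants would fall in the gap cannot be computed from the protocol.
- **Uncorrected QT may be deliberate.** Section 9.3.5.1 says "The frequency of uncorrected QT values above 500 ms will be tabulated". That is an analysis table which names the measure as uncorrected. It does not explain a trigger whose repeats are judged on QTcF.
- **Replacing QT loses something at slow heart rates.** True: at 50 bpm, without a 60 ms rise, repeats would start at QTcF 500 ms and no longer at about 471 ms. The loss is small because the later actions are judged on corrected QT.

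**Conclusion.** The point holds. Limb (b) of both trigger paragraphs in 8.3.3 is on a different scale from the repeat checks, the continuous-monitoring criterion and the withdrawal rule. In Part B participants with baseline QTcF above 440 and up to 490 ms, and heart rate above 60 × (QTcF/500)^3 bpm, a single QTcF above 500 ms mandates no confirmation. The first mandatory repeat comes 10 ms late at baseline 450 ms (65 bpm and above), 20 ms late at 460 ms (70 bpm and above), and up to 50 ms late at 490 ms (about 80 bpm and above). There is no gap at baseline 440 ms or below, or at 60 bpm or below.

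This rests on the Fridericia formula, on assumed heart rates, and on reading the trigger as written. It does not show that any participant would go unprotected, since the protocol has discretionary safeguards. It is a correction that should be made, because it concerns a safety procedure that sites carry out directly from the protocol.

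**What to change.** In limb (b) of both the single-ECG and the triplicate-ECG paragraphs of 8.3.3, change QT to QTcF, so that the absolute criterion is QTcF of at least 500 ms. This matches the continuous-monitoring paragraph, and every single ECG above the absolute threshold in 7.1.3 then prompts the two confirmatory tracings, subject to the existing over-read provision.

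If the sponsor wants to keep the earlier prompt at slow heart rates, the limb can read QT or QTcF of at least 500 ms, provided the repeat and stopping rules name the measure that applies to each.

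The cost is one word in two sentences and a few extra repeat ECGs, set against the loss of the earlier prompt below 60 bpm if QT is simply replaced.

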8.3.3.1. Part A

Triplicate 12--lead ECGs will be obtained approximately 2 to 4 minutes apart; the average of the triplicate ECG measurements collected at each nominal time point on Day 1 will serve as each participant's -time-controlled baseline QTcF value.

8.3.3.2. Part B

Single ECGs will be collected as per SoA. A triplicate ECG will be collected on Day 1. ECGs should be performed prior to 6MWT.

8.3.4. Continuous Cardiac Monitoring by Telemetry (Part A only)

Telemetry will be collected in Part A Cohorts (Cohorts 1-8) only. All abnormal rhythms will be recorded and reviewed by the investigator for the presence of rhythms of potential clinical concern. The time, duration, and description of any clinically significant events will be recorded in the CRF/DCT. In addition, a printed record of the tracing(s) of the clinically significant rhythm(s) will be made and retained with other source documents.

Telemetry should be collected using a centralized system that also allows for the storage and advanced analysis of all recorded data in order to preserve important events for future evaluations. Holter monitoring should not be used in parallel with continuous cardiac monitoring by telemetry, unless it is the only means of data storage available at the investigator site, or verifiable arrhythmia quantification is required.

To establish a baseline, telemetry should be recorded for at least 2 hours prior to dosing while participants are awake. This may be done immediately prior to dosing or at some 2-hour continuous interval in the 24 hours prior to dosing, as long as the recording is performed when the participant is awake. Telemetry may be stopped within a reasonably short period of time prior to dosing, in order to avoid interference with study operations conducted immediately before dosing. However, it is expected that the telemetry leads will be in place and the system connected prior to dosing. Post-dose telemetry will continue for 2 hours after dosing on Study Day 1 and for 2 hours on Study Day 5 and 8.

8.3.5. Clinical Safety Laboratory Assessments

See Appendix 2 for the list of clinical safety laboratory tests to be performed and the SoA for the timing and frequency. All protocol-required laboratory assessments, as defined in Appendix 2, must be conducted in accordance with the laboratory manual and the SoA. Unscheduled clinical laboratory measurements may be obtained at any time during the study to assess any perceived safety issues.

The investigator must review the laboratory report, document this review, and record any clinically significant changes occurring during the study in the AE section of the CRF. Clinically significant abnormal laboratory test findings are those that are not associated with the underlying disease, unless judged by the investigator to be more severe than expected for the participant's condition.

All laboratory tests with values considered clinically significant and abnormal during participation in the study or within 5 half-lives after the last dose of study intervention should be repeated until the values return to normal or baseline or are no longer considered clinically significant by the investigator or study medical monitor.

If such values do not return to normal/baseline within a period of time judged reasonable by the investigator, the etiology should be identified and the sponsor notified.

See Appendix 6 for suggested actions and follow-up assessments in the event of potential DILI.

PFIZER CONFIDENTIAL CT02-GSOP Clinical Protocol Template Phase 1 2 3 4 (14 April 2023) Page 103 See Appendix 7 for instructions for laboratory testing to monitor kidney function and reporting laboratory test abnormalities.

Participants may undergo random urine drug testing at the discretion of the investigator. Drug testing conducted prior to dosing must be negative for participants to receive study intervention.

8.3.5.1. Alternative Facilities for Clinical Safety Laboratory Assessment

Protocol-specified safety laboratory evaluations may be conducted at a local laboratory, during a mobile visit, or at-home if permitted by local regulations. The local laboratory may be a standalone institution or within a hospital. The following safety laboratory evaluations may be performed at a local laboratory:

- Hematology;
- Blood chemistry;
- Urinalysis;
- Coagulation;
- HIV, HBV DNA (see Appendix 2);
- Pregnancy test.

If a local laboratory is used, qualified study site personnel must order, receive, and review results. Site staff must collect the local laboratory reference ranges and certifications/ accreditations for filing at the site. Laboratory test results are to be provided to the site staff as soon as possible. The local laboratory reports should be filed in the participant's source documents/medical records. Relevant data from the local laboratory report should be recorded on the CRF.

8.3.6. Pregnancy Testing

A urine or serum pregnancy test is required at screening. Following screening, pregnancy tests may be urine or serum tests, and must have a sensitivity of at least 25 mIU/mL. Pregnancy tests will be performed in WOCBP at the times listed in the SoA. Following a negative pregnancy test result at screening, appropriate contraception must be commenced and a second negative pregnancy test result will be required at the baseline visit prior to starting the study intervention. Pregnancy tests will also be done whenever 1 menstrual cycle is missed during the active treatment period (or when potential pregnancy is otherwise suspected) and at the end of the study. Pregnancy tests may also be repeated if requested by IRBs/ECs or if required by local regulations. If a urine test cannot be confirmed as negative (eg, an ambiguous result), a serum pregnancy test is required. In such cases, the participant must be excluded if the serum pregnancy result is positive.

8.3.6.1. At-Home Pregnancy Testing

If a participant requiring pregnancy testing cannot visit a local laboratory, a home urine pregnancy testing kit with a sensitivity of at least 25 mIU/mL may be used by the participant to perform the test at-home, if compliant with local regulatory requirements. The pregnancy test outcome should be documented in the participant's source documents/medical records and relevant data recorded on the CRF. Confirm that the participant is adhering to the contraception method(s) required in the protocol.

8.3.7. Anaphylaxis Reaction Monitoring

Participants will be monitored for at least 60 minutes after IP administration on dosing days for signs and symptoms of potential anaphylaxis.

All anaphylactic reactions will be assessed by the Pfizer clinical team according to Sampson's criteria.¹⁶

8.3.8. Injection Site Reactions

An ISR observed at the clinical study site or reported by a participant after they leave the investigative site (delayed reaction) should be reported as an AE. Injection site reaction manifestations including but not limited to erythema, swelling, bruising, pain, or pruritus should be reported in the database. ISR manifestations should be treated according to the investigator's standard of care.

8.3.9. Interferon Gamma Release Assay Tuberculin Test (Screening only)

All participants will be screened for infection with TB using an approved IGRA TB assay.

If the results of the IGRA are indeterminate, the test may be repeated, and if a negative result is obtained, enrollment may proceed. A positive test on repeat is exclusionary.

Participants with repeat indeterminate IGRA results may be enrolled after consultation with pulmonary or infectious disease specialist that determines low risk of infection (ie, participant would be acceptable for immunosuppressant (eg, anti-TNF) treatment without additional action).

Participants adequately treated in the opinion of an appropriately qualified personnel (eg, a pulmonary or infectious disease specialist, or locally acceptable expert as defined by local guidelines) for latent and/or active tuberculosis infection may be enrolled regardless of IGRA results provided the treatment is well documented in the participant's medical records and/or source documentation prior to enrollment in the study and a negative chest x-ray is secured.

A participant who is currently being treated for active or latent TB infection must be excluded. See Appendix 2.

8.3.10. HIV (Screening only)

All participants will be screened for HIV. See Appendix 2.

PFIZER CONFIDENTIAL CT02-GSOP Clinical Protocol Template Phase 1 2 3 4 (14 April 2023) Page 105

